1.0 Study Summary

Study Title	Assessment of Sous Vide Water Baths for Acute Rewarming of Frostbitten Extremities
Study Design	Patients with acutely frostbitten hands or feet presenting to the emergency department will be consented to participate in the study. An ANOVA sous vide device will be attached to a water basin and set at 38°C. Two thermometers will continuously monitor water bath temperatures and the readings from the thermometers and sous vide device will be recorded every two minutes. The frostbitten extremity will remain in the circulating warm water bath for 30 minutes, at which time the extremity will be evaluated to see if rewarming is complete (warm to touch, pliable tissue). Tissue that is still frozen will be placed back into the water bath for an additional 30 minutes, at which time they will be reassessed. Medical providers directly involved in the care of the patient will fill out a survey regarding viability of this method and ease of use.
Primary Objective	To assess the ability of sous vide rewarming in maintaining constant water bath temperatures and efficacy in rewarming the acutely frostbitten extremity.
Secondary Objective(s)	To determine the ease of use of sous vide water bath rewarming in the acutely frostbitten extremity.
Research Intervention(s)/ Invest. Agent(s)	ANOVA Precision® Cooker sous vide device
IND/IDE #	NA
Study Population	Patients presenting to the emergency department with acute frostbite requiring rewarming; Providers to conduct rewarming, and complete a survey
Sample Size	1-5 patients locally, with anticipation of multicenter collaboration at 5-10 additional locations with similar enrollment goals.
Study Duration for individual participants	1-2 hours
Study Specific Abbreviations/ Definitions	SVD – sous vide device, SVR – sous vide rewarming

PROTOCOL TITLE: Assessment of Sous Vide Water Baths for Acute Rewarming of Frostbitten Extremities.

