 - The blood pressure cuff used in the standard emergency department assessment of vital signs will be placed on an extremity that is not currently being rewarmed, whenever possible, to avoid constricting blood flow to the affected tissue.
- *Data Collection:*
 - Prior to rewarming, physical examination of the patient, including the frozen extremity, will be completed and documented in the EPIC/EMR chart by the provider.
 - Two thermometers, placed in the rewarming basin, will continuously monitor the water temperature. The temperature reading on both thermometers as well as the SVD will be recorded on a paper data sheet by a trained provider at 2-minute intervals until the 30 minutes of treatment are complete.

PROTOCOL TITLE: Assessment of Sous Vide Water Baths for Acute Rewarming of Frostbitten Extremities.

- The researcher will repeat an exam, assessing all extremities being treated by SVR, at 30 minutes to determine warmth and pliability of the tissue, confirming thaw. Rewarming will be considered complete if the affected tissue becomes red or purple, soft, and pliable. The same rewarming criteria applies for all extremities.
 - The provider will be asked to fill out a survey on all acute frostbite patients whom consent to the study protocol, as well as those that do not.
 - *The source records that will be used to collect data about subjects. (Attach all surveys, scripts, and data collection forms.) If there are plans for long-term follow-up (once all research related procedures are complete), what data will be collected during this period.*
 - The patient's age and sex will be recorded. The physical examination and pertinent medical information will be reviewed to confirm the location and extent of the frostbite and for contributing conditions.
 - Demographics and relevant medical history will be accessed.
 - Please see attached surveys and data collection forms.
 - Enrolled subjects may be contacted via phone and myDH or local electronic medical record communication at 6 months post-enrollment to assess long term outcomes of their frostbite. Chart review to assess related complications will also occur at this time.
 - *Explain if any part of this study involves genetic analysis of biological specimens. If yes, explain whether the study is based on one the following:*
 - This study does not involve genetic analysis of biological specimens.

Provider Participation:

- *Role/Activities:*

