9.0 Study Timelines*

- *Describe:*
 - Each participant will be enrolled during the study period for this treatment, which includes the emergency department visit. The actual estimated treatment duration is 30 minutes. Some participants may exceed this and be treated for 60-90 minutes.
 - Given the incidence of frostbite and census of the Dartmouth-Hitchcock emergency department, and the requirement for the participant to have acute frostbite (currently frozen) rather than already thawed, it is expected to take the entire cold frostbite season to enroll 1-5 participants per study enrollment location.
 - The estimated date for the investigators to complete this study: Sept 11, 2023.

PROTOCOL TITLE: Assessment of Sous Vide Water Baths for Acute Rewarming of Frostbitten Extremities.

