18.0 Provisions to Monitor the Data to Ensure the Safety of Subjects*

- *Describe:*
 - *The plan to periodically evaluate the data collected regarding both harms and benefits to determine whether subjects remain safe. The plan might include establishing a data monitoring committee and a plan for reporting data monitoring committee findings to the IRB and the sponsor.*
 - The data will be reviewed by the local PI each time a subject participates in the study, to confirm standard process and to assess for reported adverse events.
 - As the lead site, we will review all data entered into the database for completeness.
 - *What data are reviewed, including safety data, untoward events, and efficacy data.*
 - Signed informed consent, temperature recordings, water bath treatment time required to achieve rewarming, and adverse events will be reviewed.
 - *How the safety information will be collected (e.g., with case report forms, at study visits, by telephone calls with participants).*
 - Adverse events will be recorded on the data collection form during the treatment of the subject in the emergency department.

PROTOCOL TITLE: Assessment of Sous Vide Water Baths for Acute Rewarming of Frostbitten Extremities.

- Adverse events across all sites will be reviewed at a monthly meeting of collaborating sites.
- *The frequency of data collection, including when safety data collection starts.*
 - Data collection will commence when the subject is treated in the emergency department. Data will be reviewed for safety issues after each subject.
- *Who will review the data.*
 - The PI will review the safety data.
- *The frequency or periodicity of review of cumulative data.*
 - The PI will review cumulative data after each subject.
- *The statistical tests for analyzing the safety data to determine whether harm is occurring.*
 - With an expected subject size of 1-5 study participants in each study location, safety data will be reviewed after each subject participates. There will be no need to make estimations.
- *Any conditions that trigger an immediate suspension of the research.*
 - If 1 or more unanticipated adverse events are considered possibly attributable to the use of the SVD, the study will be put on hold pending review of the incident.
- *Describe the procedures for unblinding study therapy on a subject, including documentation of this in the subject's source document.*

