19.0 Provisions to Protect the Privacy Interests of Subjects

- *Describe the steps that will be taken to protect subjects' privacy interests. "Privacy interest" refers to a person's desire to place limits on whom they interact or whom they provide personal information.*

PROTOCOL TITLE: Assessment of Sous Vide Water Baths for Acute Rewarming of Frostbitten Extremities.

- Patients who may meet the enrollment criteria will be approached and asked if they are willing to learn about a research study taking place that they may qualify for. If the patient is not interested they will receive the current standard of care treatment.
- *Describe what steps you will take to make the subjects feel at ease with the research situation in terms of the questions being asked and the procedures being performed. “At ease” does not refer to physical discomfort, but the sense of intrusiveness a subject might experience in response to questions, examinations, and procedures.*
- Potential subjects will have the traditional method of rewarming explained as well as an explanation of how SVR works. They will be informed that research is voluntary and they can withdraw at any point.
- *Indicate how the research team is permitted to access any sources of information about the subjects.*
- The study team will be permitted to access the emergency department chart of the consented subjects to be able to record de-identified sex, age, frostbite location, further information about the case or any adverse event, and patient outcomes. The subject provides consent for this access as part of the informed consent process.

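### The 6-month complication review in section 6.0 is not carried into the participation, adverse-event and chart-access sections, and no step collects harm between ED discharge and 6 months

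*Combined protocol and SAP*

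**What the plan says.** Section 6.0 (Data Collection) has two 6-month elements. Contact is optional: "Enrolled subjects may be contacted via phone and myDH or local electronic medical record communication at 6 months post-enrollment to assess long term outcomes". Chart review is not: "Chart review to assess related complications will also occur at this time".

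Other sections describe a shorter study:

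- Section 1.0, in the row "Study Duration for individual participants", gives 1-2 hours.
- Section 9.0 says "Each participant will be enrolled during the study period for this treatment, which includes the emergency department visit" and lists no 6-month step. It also says "The estimated date for the investigators to complete this study: Sept 11, 2023".
- Section 18.0 says "Adverse events will be recorded on the data collection form during the treatment of the subject in the emergency department". The local principal investigator reviews data after each subject, and the sites review adverse events together monthly. One or more unanticipated adverse events that may be due to the device put the study on hold. The rule sets no time limit.
- Section 19.0 says "The study team will be permitted to access the emergency department chart of the consented subjects". The same sentence gives as purposes "further information about the case or any adverse event, and patient outcomes".
- Section 14.0 lists reasons for withdrawing a subject without consent. They include two consecutive bath readings over 42°C and pain beyond that expected from rewarming. It then says that withdrawal ends further data collection.

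**The concern.** The protocol recognises that outcomes after the ED visit matter, but the sections that would make the follow-up work were not written around it. Section 15.0 names hot-water burns and electrical injury as hazards. Section 3.0 notes that the frostbitten extremity often lacks sensation, so pain during treatment may not reveal a burn. Section 6.0 states that the device is not FDA approved for medical use. Recording adverse events during treatment is a weak way to find the harm that the protocol itself names.

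The hold needs only one qualifying event, so it depends on such events being found and passed on. If no one looks after discharge, the per-subject and monthly reviews can appear clean because of how the data were collected. Optional contact also leaves it unclear who contributes the long-term outcomes that only the patient can report.

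**Working it through.** The plan gives no sample size, power or error rate for this point, so there is no figure to reproduce. The check is a comparison of sections plus date arithmetic.

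**1. Sections side by side**

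| Element | Section 6.0 | Elsewhere |
|---|---|---|
| Length of participation | to 6 months | 1-2 hours (1.0); no 6-month step (9.0) |
| Records used | chart at 6 months | ED chart, though for adverse events and outcomes too (19.0) |
| Complications | reviewed at 6 months | adverse events recorded during ED treatment (18.0) |
| Safety review | not mentioned | after each subject and monthly; 6-month findings not listed (18.0) |
| Withdrawn subjects | not mentioned | no further data collection (14.0) |

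**2. Tracing a late event.** Suppose an injury that meets the hold criteria is recognised some days after discharge. The treatment form was completed in the ED. The per-subject review covers consent, temperatures, treatment time and recorded adverse events. The monthly meeting covers adverse events, but no step asks about earlier patients. The first planned look is the 6-month chart review, and no text says that its findings are entered as adverse events or sent to the review in section 18.0.

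**3. Window.** From 11 March to 11 September 2023 is 184 days, or 184 × 24 = 4,416 hours. Stated participation is 1/4,416 = 0.02% to 2/4,416 = 0.05% of that. This is a share of calendar time, not of risk.

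**4. Timing of the 6-month look.** A patient enrolled on 15 January is reviewed on 15 July. More generally, if enrolment runs for one season of no more than 6 months (an assumption), even the first patient's 6-month review falls at or after the end of enrolment. In that case the review alone cannot inform the hold while patients are still being treated. That lag is inherent in a 6-month assessment, which is why an earlier check is needed.

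**5. Completion date.** 11 September 2023 minus 6 months is 11 March 2023. The documents do not say when the season ends, so a range is shown. Patients per site assume 1-5 enrolled evenly from 1 November, also an assumption.

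| Assumed season end | Days after 11 March | Weeks | Share of season | Patients per site not reaching 6 months |
|---|---|---|---|---|
| 28 February | 0 | 0 | 0 | 0 |
| 31 March | 20 | 2.9 | 20/151 = 0.13 | 0.13 to 0.66 |
| 30 April | 50 | 7.1 | 50/181 = 0.28 | 0.28 to 1.38 |

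**6. Withdrawals.** Overheating of the bath and excess pain are among the withdrawal reasons in section 14.0. If the sentence ending data collection applies to them, the patients most likely to have been harmed have no 6-month review. It answers a template prompt about subjects who withdraw, so it may have been meant only for those who choose to leave. The text does not separate the two.

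**The case against.** The strongest reply is that this is a descriptive feasibility study. Six-month outcomes are neither an endpoint in section 4.0 nor part of the analysis in section 17.0. The 1-2 hours in the summary can be read as time in study procedures, since the template prompt in section 6.0 places long-term follow-up after those procedures. Section 9.0 says only that the period includes the ED visit. Section 18.0 gives a start for data collection and no end. The consent and data collection forms are not available here and may cover follow-up. All of this stands, and it makes the matter one of alignment and missing process, not of a flawed primary analysis.

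Three stronger readings are tempting, and the documents do not support them:

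- A reader might infer that late harm cannot reach the study hold. The hold has no time limit and is not restricted to events on the ED form, so an event that came to notice could trigger it. What is missing is a stated route and timing.
- A reader might infer that any 6-month statement on complications rests on an unrepresentative subset. The complication chart review is definite; only contact is optional. Selective observation can affect outcomes that depend on contact and complications treated elsewhere, but not the chart review as a whole.
- A reader might infer that section 19.0 bars later chart review. The same sentence covers adverse events and outcomes, and section 6.0 plans the review. This is an inconsistency in wording.

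**Conclusion.** The point holds in this form: section 6.0 plans a 6-month review that sections 1.0, 9.0, 18.0 and 19.0 do not carry, no step collects complications between discharge and 6 months, and no text says how a later finding becomes an adverse event under the hold rule. Section 14.0, read literally, removes the follow-up of patients stopped for safety.

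The number of events missed cannot be estimated, because the documents give no rate of late complications. The consequence is that a clean safety record after discharge would carry little information. In an estimated 5-20 cases (section 2.0), one missed event matters. Rewarming and water temperature results are unaffected. The change should be made, though the study's main aims do not depend on it.

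The completion date is secondary. It is an estimate, and the uncovered part runs from none to about 7 weeks depending on an assumed season end. A reader might also infer that patients who decline the device should be followed for 6 months. Section 6.0 seeks their consent only for demographic, water temperature and rewarming time data, so the documents do not support requiring it.

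**What to change.** 1. **Section 18.0:** state that complications learned of after the ED visit are entered as adverse events and reviewed under the existing hold rule when learned of. Add a brief chart check of earlier sous vide patients before each monthly meeting, through their 6-month point.
2. **Section 6.0:** change *may* be contacted to *will* be contacted for all enrolled sous vide patients, and report how many were reached.
3. **Sections 19.0, 1.0 and 9.0:** extend chart access to records through 6 months, and state participation as the ED visit plus follow-up.
4. **Section 14.0:** reconcile it with section 6.0 so that stopping the device for safety does not by itself end safety data collection when the subject still consents. This concerns data collection only, not when treatment is stopped.
5. **Section 9.0:** restate the completion date as at least 6 months after the last enrolment.

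The cost is protocol and consent wording, a later completion date, one contact per patient and short chart checks. At six monthly checks per patient, 5-20 cases need 5 × 6 = 30 to 20 × 6 = 120 checks across all sites. Contact at 6 months becomes expected of each sous vide patient, who can still decline it. No clinical procedure is added.

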6.0 Procedures Involved*

- Patients presenting to the ED at Dartmouth-Hitchcock and external study sites with acute frostbite (tissue still frozen) of the hands and/or feet will be identified and approached for recruitment. Patients not entering the study will continue to be treated by ED providers in the traditional fashion.
- Patients recruited for the SVR study will be consented to have their circulating warm water bath(s) heated by the novel SVR method. Providers or nurses caring for the study subjects will be consented to participate and will 1) conduct the SVR procedure, and 2) complete a questionnaire. A researcher will gather SVR equipment and attach two thermometers on the basin: one on the side nearest the SVD, the other on the opposite side. The researcher will verbally walk the provider or nurse carrying out the SVR through the following steps. A 15 L Sterilite® basin will be filled to the marked line (12cm) with water from jugs at room temperature, for each frozen extremity. One extremity can be rewarmed in a single basin, with the possibility for up to four simultaneous SVR basins for a patient with frostbite of all hands and feet. The SVD will be attached to the distal edge of the basin, with one SVD per rewarming basin. The SVD will be turned on and set to maintain the bath at a constant 38°C for 30 minutes duration. The thermometers will be powered on continuously and the researcher will record temperatures simultaneously from each thermometer and the SVD every 2 minutes. At the end of the 30 minute treatment, the extremity will be assessed by the researcher for warmth and pliability. If the extremity still feels cold or frozen, an additional 30 minutes in the water bath will commence, with

PROTOCOL TITLE: Assessment of Sous Vide Water Baths for Acute Rewarming of Frostbitten Extremities.

subsequent reassessment. Rewarming will be considered complete when the affected tissue becomes red or purple, soft, and pliable.

- Patients who do not consent to SVR and elect for traditional water bath management will be asked for their consent to record the similar demographic, water temperature, and time-to rewarm data as in the SVR treatment arm. After re-warming is complete, the provider will be asked to fill out a survey regarding the ease of use and efficacy of the SVR.
- *Describe:*
 - *Procedures performed to lessen the probability or magnitude of risks.*

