 - Dual thermometers will record water bath temperature to assess for the possibility of disequilibrium in water temperature and to detect possible hot spots.
 - The treatment will be terminated if two consecutive thermometer recordings detect water temperatures of 42°C or above.
 - The rewarming process in acute frostbite is inherently painful. Pain increases when water bath temps are above 40°C. No additional discomfort is expected beyond that for frostbite rewarming, at the target temperature of 38°C. The provider can provide analgesia as indicated. The treatment will be terminated if the patient has discomfort that is deemed by the treating provider to be above that expected from rewarming frozen tissue.
 - If treatment is discontinued prior to successful rewarming, standard rewarming will occur.
 - *Explain if any part of this study involves the use of procedures that are inconsistent with the standard of care at Dartmouth-Hitchcock Medical Center.*
 - There are no parts of the study that are inconsistent with the standard of care at DHMC. The novel treatment is to assess a treatment modality that may elevate the standard of care.
 - *All drugs and devices used in the research and the purpose of their use, and their regulatory approval status.*

PROTOCOL TITLE: Assessment of Sous Vide Water Baths for Acute Rewarming of Frostbitten Extremities.

- The ANOVA Precision® Cooker is a purpose-built device to maintain a set temperature circulating water bath. The device is not FDA approved for medical use. There will be no use of a placebo.
- The study treatment takes place entirely in the ED, which allows for comprehensive assessment of protocol compliance. If a subjects opts to discontinue participation at any time during the rewarming, standard techniques for maintaining the water bath will replace the SVD.
- *Describe randomization:*
 - All patients presenting with acutely frostbitten hands or feet will be approached for inclusion in the study. There is no randomization. Any patient not consenting to the use of the SVD but willing to allow data collection will act as a control group.
- *Prior and Concomitant Therapy:*
 - Concomitant therapies, such as intravenous fluids, anti-emetics, forced air warming blanket, and analgesia, as well as other medications deemed necessary by the provider, may be given concomitantly during the treatment period.

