PROTOCOL TITLE: Assessment of Sous Vide Water Baths for Acute Rewarming of Frostbitten Extremities.

- Providers assigned to a patient in the emergency department who is determined to have acute frostbite will be targeted.
- The provider's role will be to identify an acute frostbite patient and ask their patient whether they would be interested in hearing more about and potentially participating in a study assessing a new way to rewarm their frostbitten tissue.
- If the patient agrees, the provider access the study on-call investigator list (posted in the ED provider area) and inform a researcher of the patient and need to discuss the stud and potentially enroll the patient.
- *Recruitment:*
 - Providers assigned to a patient in the emergency department who is determined to have acute frostbite.
- *Eligibility:*
 - Any provider managing a frostbite patient at the training levels of PA, APRN, resident physician, fellow, or attending physician are eligible.
- *Consent Process:*
 - Once the patient has consented to participate, the provider will be consented in an area of the emergency department separate from the patient's room, using the provider consent form.
- *Risks/Benefits:*
 - Risks to providers should be minimal. We do not anticipate providers having any difficulty with voluntary decision-making for this study.
 - Benefits to the provider may include improved work flow due to the decreased labor in maintaining a SVR water bath in comparison to manual water bath management. Additionally, participation will provide a firsthand opportunity to treat acute frostbite with a new modality that has potential for increased use in the future.
- *Data Collection:*
 - After successful completion of the SVR, providers will be asked to take a short, 6-question paper survey regarding ease-of-use of the SVR.

PROTOCOL TITLE: Assessment of Sous Vide Water Baths for Acute Rewarming of Frostbitten Extremities.

- Paper data collection forms will be kept in a locked office until transferred by the PI to a Microsoft excel file on a password-protected DH computer.

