14.0 Withdrawal of Subjects*

- Subjects will be withdrawn without their consent for safety reasons or medical necessity. Criteria as follows: If water bath temperatures are recorded at over 42°C on two consecutive readings during the

PROTOCOL TITLE: Assessment of Sous Vide Water Baths for Acute Rewarming of Frostbitten Extremities.

same treatment phase, if subject is judged by the treating clinician to have pain greater than expected for frostbite rewarming, or if a separate medical issue arises in the subject in which urgent treatment necessitates termination of the research.

- *Describe any procedures for orderly termination.*
 - The SVD will be powered off and the water bath maintained manually by medical staff.
- *Describe procedures that will be followed when subjects withdraw from the research, including partial withdrawal from procedures with continued data collection.*
 - Withdrawal from the research will preclude any further data collection. Data already collected at the time of the withdrawal will be analyzed with other study data but noted that the study terminated prematurely.

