 - While unlikely, it is possible that the SVR would not heat the water and delay time to the current practice of manual water bath management. If this were to occur, delay to therapy would be minimal as the only change in intervention would be the manual addition of warm water to the basin. It is expected that the research treatment will speed up the delivery of effective therapy.
 - Risk will be minimized by assessing the water temperature continuously. The SVR will be ceased and the manual rewarming started if the water bath does not reach the target temperature in 30 minutes, or if the water bath temperature drops below 37°C for more than 5 minutes.
 - If providers are unable to reach an on-call investigator and determine their availability within 20 minutes from the patient expressing interest in the study, standard rewarming will proceed via traditional water exchange practices.
- *If applicable, indicate which procedures may have risks to the subjects that are currently unforeseeable.*
 - Unforeseeable risks different than typical water bath rewarming, if any, would relate to SVD failure. To further minimize this unlikely event the SVD will be physically checked for any signs of wear following each utilization at

PROTOCOL TITLE: Assessment of Sous Vide Water Baths for Acute Rewarming of Frostbitten Extremities.

the time of cleaning. The SVD has been assessed by biomedical engineering at Dartmouth-Hitchcock and deemed low risk.

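### One passage ties the ease-of-use survey to successful sous vide rewarming while others do not; read literally, it leaves out stopped attempts (minor)

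*Combined protocol and SAP*

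**What the plan says.** Section 4.0 makes a survey on ease of use the secondary endpoint, and Section 2.0 includes ease of use in the hypothesis. The documents say in several places when, or for whom, the survey is completed:

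- Section 6.0, Provider Participation, Data Collection: "After successful completion of the SVR, providers will be asked to take a short, 6-question paper survey regarding ease-of-use of the SVR".
- Section 1.0, Study Design: "Medical providers directly involved in the care of the patient will fill out a survey regarding viability of this method and ease of use".
- Section 6.0, opening description of procedures: "Providers or nurses caring for the study subjects will be consented to participate and will 1) conduct the SVR procedure, and 2) complete a questionnaire". Later, in the bullet on patients who decline SVR, a further sentence places the provider survey once rewarming has finished, without saying that SVR must have achieved it.
- Section 6.0, the earlier Data Collection list: the provider is to "fill out a survey on all acute frostbite patients whom consent to the study protocol, as well as those that do not".

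The protocol foresees SVR attempts that do not run to the end. Section 6.0 states: "If treatment is discontinued prior to successful rewarming, standard rewarming will occur". Sections 6.0 and 14.0 give over-temperature readings and excess pain as reasons to stop. Section 15.0 adds failure to reach or hold temperature: "The SVR will be ceased and the manual rewarming started if the water bath does not reach the target temperature in 30 minutes", with a second condition for a bath that falls too low. Section 6.0 also allows the patient to opt out during rewarming.

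On withdrawn subjects, Section 14.0 says both "Withdrawal from the research will preclude any further data collection" and "Data already collected at the time of the withdrawal will be analyzed with other study data but noted that the study terminated prematurely". Section 17.0 plans descriptive statistics for ease of use and gives neither a denominator nor a rule for attempts without a survey.

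**The concern.** An attempt in which the device would not heat, overheated, or had to be replaced by manual rewarming says a good deal about usability. If the survey is requested only after success, the set of raters depends on the outcome of the procedure they are rating. If stopped attempts would have been rated worse, the reported ease of use is too favourable.

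The differing statements also leave room for sites to act differently. Section 1.0 anticipates 5 to 10 additional locations, and one that works from the Provider Participation text could survey a different set of attempts from one that works from the earlier Data Collection list. A rating not requested at the time may be hard to recover later.

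No test or decision rule uses the survey, so what is at stake is the accuracy of a descriptive secondary result.

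**Working it through.** **Step 1. The texts side by side.** The documents contain no ease-of-use figure to reproduce, so the first check is textual.

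| Place | Condition on the survey | Would a stopped SVR attempt be surveyed? |
|---|---|---|
| 1.0 Study Design | Provider directly involved in care | Yes |
| 6.0, procedures | Consented to run SVR and complete a questionnaire | Yes |
| 6.0, bullet on patients who decline SVR | Rewarming finished | Yes, once standard rewarming has finished the job |
| 6.0, earlier Data Collection list | All acute frostbite patients | Yes |
| 6.0, Provider Participation | SVR completed successfully | No, if read literally |

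The third row does contain a completion condition. Section 6.0 defines complete rewarming by the state of the tissue, and a stopped SVR is followed by standard rewarming. That condition can therefore be met without SVR having succeeded. Only the last row mentions SVR success.

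**Step 2. Size, under stated assumptions.** Neither a stop rate nor a response scale is given. Assume one survey per attempt and a binary easy/not easy rating. Let n be the SVR attempts started, k the stopped attempts left unsurveyed, p_s the proportion rated easy among surveyed attempts and p_o the proportion among omitted ones.

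- Reported: p_s
- All attempts: (1 − k/n) × p_s + (k/n) × p_o
- Overstatement: (k/n) × (p_s − p_o)

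Section 2.0 expects 5 to 20 cases. With k = 1:

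| p_s − p_o | n = 5 | n = 20 |
|---|---|---|
| 0 | 0.20 × 0 = 0 points | 0.05 × 0 = 0 points |
| 0.5 | 0.20 × 0.5 = 10 points | 0.05 × 0.5 = 2.5 points |
| 1 | 0.20 × 1 = 20 points | 0.05 × 1 = 5 points |

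At the upper end, 4/5 (80%) would be reported as 4/4 (100%), and 19/20 (95%) as 19/19 (100%).

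A less extreme illustration, also assumed: 90% of surveyed attempts are rated easy, and stopped attempts would be rated easy 50% or 20% of the time. With one omitted attempt, the figure over all attempts is:

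- n = 5: 0.8 × 90 + 0.2 × 50 = 82%, or 0.8 × 90 + 0.2 × 20 = 76%
- n = 20: 0.95 × 90 + 0.05 × 50 = 88%, or 0.95 × 90 + 0.05 × 20 = 86.5%

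**Step 3. Would a stopped attempt occur at all?** The chance of at least one is 1 − (1 − q)^n for an assumed stop rate q. For q = 5%, 10% and 20% it is 23%, 41% and 67% at n = 5, and 64%, 88% and 99% at n = 20.

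**Step 4. Precision.** Exact 95% intervals are 39.8–100% for 4/4 against 28.4–99.5% for 4/5, and 82.4–100% for 19/19 against 75.1–99.9% for 19/20. They overlap widely, so the point concerns the direction of a possible bias and not a particular figure.

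**The case against.** The strongest reply is that the Provider Participation sentence describes timing only. It says after, not only after, and nowhere says that stopped attempts go unsurveyed. The sentence placing the survey once rewarming has finished is built the same way and supports that reading. The earlier Data Collection list speaks of all acute frostbite patients, which includes a consenting patient whose SVR was stopped. The survey forms are not in the reviewed text, so their own instructions may settle the matter. All of this has weight and is why the point is minor. What remains is that one sentence names success, no text says which statement governs, and the literal reading is open to a site.

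Three stronger readings are tempting but not supported:

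- *Stopped attempts will count in the temperature results but not in ease of use.* Section 14.0 keeps data already collected from withdrawn subjects, but its listed criteria are over-temperature, excess pain and a separate medical issue. The failures to reach or hold temperature in Section 15.0 are not among them, so Section 14.0 does not settle how those attempts are handled.
- *Section 14.0 forbids the survey after a withdrawal.* Its bar on further data collection is written about patient subjects. Whether it reaches a provider who has consented separately is not stated.
- *The omission would go unseen.* Section 18.0 has the data reviewed after each subject and the lead site checking the database for completeness, and Section 14.0 has early terminations noted. A shortfall of surveys against attempts could be found that way, although no text says the count will be reported.

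**Conclusion.** The conflict in wording is real; its effect is conditional. Followed literally, the Provider Participation sentence in Section 6.0 leaves out stopped or failed SVR attempts, contrary to the other survey statements. The reported ease of use is then overstated if those attempts are rated worse, and unaffected if they are rated the same or if none occurs.

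The size cannot be found from the documents and may be zero. With one survey per attempt, a binary rating and one omitted attempt rated no better than the rest, the range is 0 to 20 percentage points at 5 attempts and 0 to 5 at 20. The upper ends need the largest possible rating gap.

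A reader might infer that the trial selects its raters on success by design. The documents do not show that, since the broader statements point the other way. This is a minor inconsistency to be reconciled before sites act on it.

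**What to change.** 1. **Section 6.0, Provider Participation.** Replace the opening condition with: *After every SVR attempt, whether completed, stopped early or switched to manual rewarming.* This agrees with Section 1.0 and the other survey statements in Section 6.0.
2. **Section 17.0.** State that ease of use is summarised over all SVR attempts started, giving the number of surveys received against the number of attempts and identifying the stopped ones.
3. **Section 14.0.** State whether the bar on further data collection applies to the survey of a separately consented provider, so that it agrees with the all-patients statement in Section 6.0.

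The cost is a few sentences, with IRB review of the wording, and a few more short forms. The ease-of-use figure may come out less favourable. No treatment or stopping rule changes.
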